Appendix 1.4. Censoring for Time-to-Event Data

Table 4 summarizes the censoring rules for the PFS analysis and displays censoring hierarchy for this study. Table 5 shows the general reasons for PFS censoring and where the censoring hierarchy in Table 4 comes from.

Table 3 PFS (Primary Definition) Censoring Reasons and Hierarchy

Censoring Hierarchy	Situation	Date of Event or Censor	Event / Censor
1	No baseline radiological tumor assessment available	Date of Randomization	Censored
2	New anticancer treatment started and no tumor progression	Date of previous adequate radiological assessment immediately prior to start of new therapy	Censored
3	Tumor progression (per RECIST 1.1 or mRECIST) documented after 2 scan intervals following previous adequate radiological tumor assessment	Date of previous adequate radiological assessment	Censored
4, 5	No tumor progression (per RECIST 1.1 or mRECIST) and patient lost to follow-up or withdrawal of consent	Date of last adequate radiological assessment	Censored
6	No post baseline radiological tumor assessment available and no death reported within 2 scan intervals following the date of randomization	Date of Randomization	Censored
	No post baseline radiological tumor assessment available but death reported within 2 scan intervals following the date of randomization	Date of Death	Event
7	No tumor progression (per RECIST 1.1 or mRECIST) and no death reported within 2 scan intervals following last adequate radiological tumor assessment	Date of last adequate radiological tumor assessment	Censored
	No tumor progression (per RECIST 1.1 or mRECIST) but death reported within 2 scan intervals following last	Date of Death	Event

Censoring Hierarchy	Situation	Date of Event or Censor	Event / Censor
	adequate radiological tumor assessment		
	Tumor progression (per RECIST 1.1 or mRECIST) documented within 2 scan intervals following previous adequate radiological tumor assessment	Earliest of the target, non-target and new tumor assessment dates	Event

Notes: (1) Symptomatic deteriorations (i.e., symptomatic progressions, which are not radiographically confirmed) will not be considered as progressions.
 (2) If target, non-target and new lesion assessments have different dates within a visit, then the earliest of those dates will be considered as the date of the tumor assessment if the assessment for that visit is progressive disease (PD); otherwise the latest date will be used.
 (3) Adequate radiographical tumor assessment refers to an assessment with overall response of CR, PR, SD, or PD.

Table 4 PFS Censoring Reasons and Hierarchy

Hierarchy	Condition	Censoring Reason
1	No adequate baseline assessment	No adequate baseline assessment
2	Start of new anti-cancer therapy before event.	Start of new anti-cancer therapy
3	Event more than (16 weeks+7 days) from last adequate post-baseline tumor assessment/start date	Event after missing assessments ^a
4	No event and [withdrawal of consent date ≥ start date OR End of study (EOS) = Patient refused further FU]	Withdrawal of consent
5	No event and lost to follow-up in any disposition page	Lost to follow-up
6	No event and [EOS present OR disposition page for any EPOCH after screening says patient will not continue into any subsequent phase of the study] and no adequate post-baseline tumor assessment	No adequate post-baseline tumor assessment
7	No event and none of the conditions in the prior hierarchy are met	Ongoing without an event

^a More than (16 weeks+14 days) after last adequate tumor assessment. <Note: This should correspond to 2 or more missing assessments using the nominal schedule of assessments but best to describe directly as 16 weeks to match on how the analyses are performed as per the table above>

Date of Last Contact for Overall Survival

The date of last contact will be derived for patients not known to have died at the analysis data cutoff date using the latest complete date (non-imputed) among the following:

- All patient assessment dates (e.g., blood draws [laboratory, PK], vital signs, performance status, ECG, tumor assessments, concomitant radiation, surgery)
- Start and end dates of follow-up anti-cancer therapies
- AE start and end dates
- Last date of contact where “Subject Remains in Follow-up” collected on the “Survival Follow-up” eCRF (do not use date of survival follow-up assessment unless status is alive)
- Study drug start and end dates
- Randomization date
- Date of discontinuation on disposition eCRF pages (do not use if reason for discontinuation is lost to follow-up or death).

Note:

- This list is not all inclusive and should be agreed upon by the study team according to the data collected in the CRF
- Only dates associated with patient visits or actual examinations of the patient should be used. Dates associated with a technical operation unrelated to patient status (e.g., the date a blood sample was processed) should not be used.
- Assessment dates after the cutoff date will not be applied to derive the last contact date.

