### 5.10 Follow Up After Treatment Discontinuation

For both the phase Ib and phase II portions of the study, the follow-up phase of the study will begin after the EOS study visit has been completed. Patients will be followed for specified clinical endpoints (both primary safety and secondary exploratory efficacy endpoint), and other important information such as post-protocol therapy.

As specified in Section 5.7.2, per-protocol imaging (every 8 weeks/56 days) should continue until criteria for disease progression according to both RECIST 1.1 and mRECIST for HCC are met.

There are no further visits required specifically for the study after the EOS visit, with the exception of radiologic assessments every 8 weeks until progression of disease is documented according to both RECIST 1.1 criteria and mRECIST for patients with HCC criteria.

The clinical parameters and endpoints for follow-up after a patient permanently discontinues study drug (either BBI608 or BBI503) administration are specified in table below, as is the recommended follow up frequency. Follow-up and information collection is intended to be accomplished through review of the local medical record system by site study staff and/or study CRAs-Monitors. Contact with the primary oncologist and/or primary care physician for a given patient may also be required.

Table 3: Clinical Parameters for Post-Protocol Therapy Follow-Up

Endpoint	Description	Follow-Up Frequency
Performance Status Decline	First date when ECOG performance status of $\geq 3$ is documented, if possible	Evidence for clinical endpoints
Subsequent Therapy	Names and dates of anti-cancer treatment administered after permanent study drug (either BBI608 or BBI503) discontinuation. "Clinical Trial" can also be used if agent name is not publically available	will be assessed monthly for the first 6 months after discontinuing study drug (either BBI608 or BBI503)  Then,  Quarterly from 6 months to 18
Objective Disease Progression following subsequent therapy	Date criteria for RECIST 1.1 and/or mRECIST for HCC categorization of "PD" are met after starting any post-protocol therapy, if possible*	months after discontinuing study drug (either BBI608 or BBI503)  Then,  Semi-annually thereafter
Survival	Date of death due to any cause	Semi-aminary mereaner

\*Passive follow-up only of radiologic imaging obtained following initiation of any post-protocol therapy

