2.2. Secondary Endpoints

- Plasma concentration of napabucasin administered in combination with sorafenib.
- Plasma concentration of amcasertib administered in combination with sorafenib.
- Pharmacodynamics parameters (or biomarkers level in archival tissues) of napabucasin administered in combination with sorafenib.
- Pharmacodynamics parameters (or biomarkers level in archival tissues) of amcasertib administered in combination with sorafenib.

- Progression-Free Survival (PFS) by both RECIST and mRECIST in phase II.

PFS is defined as the time from the date of randomization to the date of first documentation of PD or death due to any cause, whichever occurs first.

PFS censoring rules are provided in Appendix 1.4: Censoring for Time-to-Event Data.

- Overall Survival (OS)

OS is defined as the time from the date of randomization to the date of death. Patients without documentation of death at the time of analysis will be censored at the date last known to be alive.

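### Rows 4, 5 of the SAP's first PFS censoring table censor lost or withdrawn patients without excluding a known death, contrary to the table's source and to the PFS definition

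*SAP*

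**What the plan says.** SAP 2.2 ends PFS at "the date of first documentation of PD or death due to any cause, whichever occurs first". The censoring rules are in SAP Appendix 1.4, in two tables. The text there calls them Tables 4 and 5 while their captions say 3 and 4, so I call them first and second in order of appearance.

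- **Role of the tables.** On the first: "Table 4 summarizes the censoring rules for the PFS analysis and displays censoring hierarchy for this study". The second is described as "where the censoring hierarchy in Table 4 comes from".
- **First table, rows 4, 5.** The condition is "No tumor progression (per RECIST 1.1 or mRECIST) and patient lost to follow-up or withdrawal of consent". The result is censoring at the last adequate radiological assessment. Death is not mentioned.
- **First table, lower down.** Two unnumbered event rows appear with rows 6 and 7. One covers patients with no scan after baseline: "No post baseline radiological tumor assessment available but death reported within 2 scan intervals following the date of randomization". The other reads "No tumor progression (per RECIST 1.1 or mRECIST) but death reported within 2 scan intervals following last" adequate assessment. Both give an event on the date of death.
- **Second table, rows 4 and 5.** Both require that there be no event. Row 5, for example, reads "No event and lost to follow-up in any disposition page".

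SAP 6.4 censors patients who withdraw or are lost before PD or death is documented, and refers to Appendix 1.4 for the PFS rules. It does not say what happens when a death is learned of afterwards.

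**The concern.** A patient marked as lost can later be found to have died. Protocol 5.10 says "Follow-up and information collection is intended to be accomplished through review of the local medical record system" by site staff or monitors, and it asks for survival to be checked monthly for the first six months after study drug stops. If rows 4, 5 are applied as worded and in order, that death never reaches the event row, and PFS ends as censored at the last scan.

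Note 1 under the first table excludes symptomatic deterioration without radiographic confirmation as progression. For a patient who declines and has no further imaging, death is therefore the only PFS event left to record. Censoring such a patient at the last good scan is informative. The same death would still count for OS, because SAP 2.2 censors OS only where no death is documented. At stake are the PFS curve and PFS-4, the one anti-tumor measure named in the phase II sample-size text (Protocol 10.5, SAP 3.2.3).

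**Working it through.** No figure in the plan depends on this rule, so there is none to reproduce. The check runs test patients through both tables and then sizes the difference.

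**Inputs.** Scans are every 56 days (Protocol 5.7.2), so two scan intervals are 2 × 56 = 112 days. The late-event limit in row 3 of the second table is 16 weeks + 7 days = 119 days. Its footnote says 16 weeks + 14 days = 126 days. The target is 30 patients in each of Arms 1 and 3 (Protocol 10.3). Four months is taken as 16 weeks (Protocol 3.3), day 112. Randomization and first dose are treated as the same day.

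**Rule check.** All test patients have an adequate baseline, no PD and no new therapy. The first table is read in its stated order.

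| Last scan | Lost or withdrawn | Death | First table | Second table |
|---|---|---|---|---|
| day 56 | day 70 | day 98 | censored day 56 (rows 4, 5) | event day 98 |
| day 112 | day 120 | day 200 | censored day 112 (rows 4, 5) | event day 200 |
| day 56 | day 70 | none | censored day 56 | censored day 56 |
| day 56 | no | day 100 | event day 100 | event day 100 |
| day 56 | day 70 | day 200 | censored day 56 | censored day 56 (row 3) |

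In the first two lines the death falls 98 − 56 = 42 and 200 − 112 = 88 days after the last scan, inside either limit. In the last line the gap is 144 days, outside it. The split produced by rows 4, 5 is thus confined to lost or withdrawn patients whose death is known and falls inside the window.

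**Size (assumed counts).** Take 30 patients, with 8 progressions at day 56, 5 at day 112, and k patients last scanned at day 56 who are lost and die at day 98. The rest are event-free. Kaplan-Meier at day 112:

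- Deaths counted: (30 − 8 − 5 − k)/30.
- Deaths censored at day 56: 22/30 × (17 − k)/(22 − k).

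| k | Counted | Censored | Difference |
|---|---|---|---|
| 1 | 16/30 = 0.533 | 22/30 × 16/21 = 0.559 | 2.5 points |
| 2 | 15/30 = 0.500 | 22/30 × 15/20 = 0.550 | 5.0 points |
| 3 | 14/30 = 0.467 | 22/30 × 14/19 = 0.540 | 7.4 points |

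With 6 and 6, or 10 and 5, progressions at the two scans, the differences are 2.5, 4.8 and 7.1 points.

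The upward direction holds for deaths before the four-month mark. If the single patient died at day 150 instead, PFS-4 would be 17/30 = 0.567 when the patient stays at risk and 0.559 when censored at day 56. That is a small shift the other way, although the curve after day 150 would still be too high.

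**The case against.** The strongest reply is that the SAP already shows what it intends. The first table only summarizes; its declared source requires no event; the definition counts any death; and the first table has its own death rows. A careful programmer could supply the missing condition. That stands, and it means a reader should not infer that the SAP deliberately discards these deaths. It does not remove the defect, because the first table is the one that states event and censoring dates, and its rows 4, 5 say otherwise.

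Next, the numbered ranks may order censoring reasons only, since the event rows carry no number and rank 7 in the second table means ongoing without an event. This is a fair reading. On it the first table does not override its death row, but it places one patient in both a censored row and an event row without saying which prevails. The edit is still needed.

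Three stronger readings are tempting but not supported:

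- **Patients who leave before any post-baseline scan.** One might set rows 4, 5 against the event row at row 6. But rows 4, 5 censor at an adequate assessment, which Note 3 defines by an overall response of CR, PR, SD or PD. Such a patient has none, so those rows give no usable date, while the row-6 companion addresses exactly this case.
- **Deaths after consent is withdrawn.** Protocol 5.10 describes record review after treatment ends. Nothing cited says that records are searched after withdrawal of consent. The lost-to-follow-up case is the firmer example.
- **Bias in favour of one arm.** Unequal losses in an open-label study could produce this, but the documents give no loss rates by arm.

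Finally, PFS is a secondary endpoint, SAP 3.1 rules out hypothesis testing, and the shift is modest beside an exact 95% interval of about 31% to 69% for 15/30. All of that is correct and limits the consequence.

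**Conclusion.** The point holds as a conflict between a stated rule and both its source and the endpoint definition. As worded and in the stated order, rows 4, 5 of the first table turn a known PFS event into a censored observation for lost or withdrawn patients with a death inside the window. The contradiction rests on the text alone.

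The size does not. About 2.5 to 7 percentage points on PFS-4 for one to three patients in a 30-patient arm assumes those counts, the progression pattern, death before four months, and a Kaplan-Meier estimate of PFS-4. The documents give no number of such deaths. Descriptive PFS and PFS-4 estimates are affected, and no test or decision rule is.

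The late-event limit is also inconsistent, at 112, 119 and 126 days. For that reason, adding only a two-scan-interval death exclusion to rows 4, 5 would not make the tables agree: a lost patient who dies 115 days after the last scan would still be censored in the first table and be an event in the second.

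**What to change.** 1. In rows 4, 5 of the first PFS table, replace the no-progression condition with the second table's condition: *no event (neither PD nor death)*, and lost to follow-up or consent withdrawn. A death known from permitted sources within the allowed window is then an event whatever the disposition reason. Later deaths fall to the existing censoring rows.
2. Make SAP 6.4 say the same, including for a death learned of after the patient was recorded as withdrawn or lost.
3. State one late-event window in days and use it in both tables and the footnote.

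The cost is a phrase in the table, a sentence in 6.4 and one harmonized limit. No new data are needed. The downside is that PFS may look slightly less favourable.

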#### **9.3.1** New Lesions in RECIST 1.1

New lesions should be unequivocal and not attributable to differences in imaging modality or techniques. Findings from processes not directly related to tumor progression should also be excluded.

If a new lesion is equivocal, or uncertain as to etiology, protocol treatment should continue until a subsequent radiologic image is obtained at least 4 weeks later. If repeat imaging confirms the original diagnosis of new lesion, then the original scan date should be used for the radiologic diagnosis of progressive disease.

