#### **9.3.2** New Lesions in mRECIST for HCC

The approach to a potential new lesion when assessing response according to mRECIST for HCC is outlined below:

- A newly detected hepatic nodule will be classified as HCC if its longest diameter is at least 1 cm and the nodule shows the typical vascular pattern of HCC on dynamic imaging.
- Liver lesions larger than 1 cm that do not show a typical vascular pattern can be diagnosed as HCC if repeat radiologic imaging shows at least 1-cm-interval growth.
- If repeat imaging confirms the original diagnosis of new lesion, then the original scan date should be used for the radiologic diagnosis of progressive disease.

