Appendix 1.3. Evaluation of Best Overall Response

Target lesions	Non-Target lesions	Evaluation of New lesions	Overall response
CR	CR	No	CR
CR	Non-CR/non-PD	No	PR
CR	Not evaluated	No	PR
PR	Non-PD or not all evaluated	No	PR
SD	Non-PD or not all evaluated	No	SD
PD	Any	Yes or No	PD
Any	PD	Yes or No	PD
Any	Any	Yes	PD

The best overall response (BOR) is the best response recorded from start date until disease progression or start of new anti-cancer therapy. BOR is determined by the following order:

CR: One objective status of CR documented before progression or start of new anti-cancer therapy.

PR: One objective status of PR documented before progression and start of new anti-cancer therapy, but not qualifying as CR.

SD: At least one objective status of SD documented at least (8 weeks – 7 days) after start date and before progression and the start of new anti-cancer therapy but not qualifying as CR or PR.

PD: Progression documented within (16 weeks + 7 days) after start date and not qualifying as uCR, uPR, or SD.

NE: All other cases. Note that reasons for NE should be summarized and the following reasons could be used:

- Early death (Note: death prior to (8 weeks – 7 days) after start date)
- No post-baseline assessments
- All post-baseline assessments have overall response NE
- New anti-cancer therapy started before first post-baseline assessment
- SD too early (< (8 weeks – 7 days) after start date))
- PD too late (> (16 weeks + 7 days) after start date)

Special and rare cases where BOR is NE due to both early SD and late PD will be classified as ‘SD too early’.

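### The SAP does not carry over the protocol's rule that a confirmed new lesion is dated to the scan where it was first seen, so PFS and disease control depend on how sites leave that first scan recorded

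*SAP*

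**What the plan says.** **Protocol.** Section 9.3.1 (RECIST 1.1) covers a new lesion that is equivocal or of uncertain origin: "protocol treatment should continue until a subsequent radiologic image is obtained at least 4 weeks later". If the repeat scan confirms it, "then the original scan date should be used for the radiologic diagnosis of progressive disease". Section 9.3.2 (mRECIST) has the same dating rule: "If repeat imaging confirms the original diagnosis of new lesion, then the original scan date should be used". It states no minimum interval before the repeat scan.

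**SAP, PFS.** Section 2.2: "PFS is defined as the time from the date of randomization to the date of first documentation of PD or death due to any cause". In the Appendix 1.4 censoring table, the date for a progression event is "Earliest of the target, non-target and new tumor assessment dates". Note 2 sets the scope of that rule: "If target, non-target and new lesion assessments have different dates within a visit, then the earliest of those dates will be considered". It applies when the assessment for that visit is PD. Otherwise the latest date in the visit is used.

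**SAP, BOR.** Appendix 1.3 gives SD on this condition: "At least one objective status of SD documented at least (8 weeks – 7 days) after start date and before progression". DCR counts CR, PR and SD, and SAP 2.1 names it, with ORR, as a phase II primary endpoint.

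The SAP does not mention equivocal new lesions. Its Appendices 1.1 to 1.3 restate the response tables of protocol Section 9 but leave out Section 9.3.

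**The concern.** A deferred new-lesion call involves two scans: the one where the lesion first appears and the one that settles what it is. The protocol puts progression at the first. The SAP looks for the visit at which PD is recorded and takes the earliest date inside that visit. A first scan that was called SD while the lesion was equivocal is a different visit, so the SAP rule does not reach it.

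The situation is foreseeable. Protocol 9.3 warns that underlying cirrhosis complicates new-lesion calls in HCC and that these calls weigh heavily on progression endpoints. Under 9.3.2, a liver lesion over 1 cm without the typical vascular pattern can be called HCC only after growth on a later scan. The trial is open label and site staff document the assessments, so the date should come from a stated rule and not from whether a site goes back to change an entry.

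At stake are the PFS date, BOR and DCR for the affected patients, and sometimes PFS-4, each under both response criteria.

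**Working it through.** The plan states no figure on this point, so there is none to reproduce. The check is date arithmetic, followed by an illustration of size.

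**Inputs**
- Scans every 56 days from first sorafenib dose, ±7 days for each scan (protocol 5.7.2).
- Repeat scan at least 28 days later (protocol 9.3.1; none stated in 9.3.2).
- SD counts from 8 weeks − 7 days = day 49. BOR of PD requires progression by 16 weeks + 7 days = day 119 and no qualifying SD or response (SAP Appendix 1.3).
- Target of 30 patients each in Arms 1 and 3 (protocol 10.3).
- PFS-4 is taken at 4 months, equated with 16 weeks after randomization in protocol 3.3. Treatment starts within 72 hours of randomization (protocol 4.3).

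**1. Delay for one affected patient whose first scan stays non-PD**
- Minimum under RECIST 1.1: 28 days.
- Confirmation at the next scheduled scan: nominally 56 days. With both windows, 56 − 14 = 42 to 56 + 14 = 70 days.
- No maximum is stated, and a missed scan would lengthen it.

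**2. Week-8 lesion and DCR**

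The first scan falls on day 49 to 63 and is recorded as SD. PD is confirmed between day 77 (49 + 28) and day 119.
- SAP as written: the SD is at or after day 49 and before the recorded PD, so BOR is SD and the patient counts in DCR. The PD falls within two scan intervals of the first scan, so it is an event at the confirming scan.
- Protocol date: PD on day 49 to 63 with no earlier SD, so BOR is PD and the patient does not count.
- Effect: 1/30 = 3.3 points. For example, 15/30 = 50.0% (exact 95% CI 31.3 to 68.7) becomes 16/30 = 53.3% (34.3 to 71.7).
- If the first scan was entered as NE, with no other SD or response, PD by day 119 gives BOR PD and later PD gives NE. Neither counts in DCR. The DCR effect therefore needs an entry of SD or better.

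**3. PFS-4**

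The week-16 scan falls nominally 112 to 115 days after randomization, because dosing may start up to 3 days later. The estimate changes only if the two scans fall on either side of the cut-off.
- Cut-off at 16 weeks (day 112): a lesion first seen at week 8 and confirmed at week 16 crosses only if the week-16 scan is after day 112. A lesion first seen at week 16 crosses only if that scan is on or before day 112.
- Cut-off at 4 calendar months (4 × 30.44 ≈ 122 days): a lesion first seen at week 16 and confirmed at least 28 days later normally crosses. A lesion first seen at week 8 and confirmed at week 16 normally does not.
- A lesion first seen at week 24 or later moves neither DCR nor PFS-4.

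**4. Arm-level illustration (assumptions, not document figures)**

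Progression times are exponential with a median of 5.5 months (167.4 days), borrowed from the sorafenib TTP in protocol 1.4. Scans are every 56 days from randomization. A share f of progressions is affected, every affected first scan is recorded as SD and never revised, and the delay d is 28 or 56 days.
- Share read as progressed at week 8: 1 − exp(−ln 2 × 56/167.4) = 20.7%.
- Free of progression after week 16: exp(−ln 2 × 112/167.4) = 62.9%. First read as progressed at week 16: 79.3 − 62.9 = 16.4%.
- Mean PFS shift = f × d. DCR shift = f × 20.7 points. PFS-4 shift = f × 16.4 points.

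| f | Mean PFS shift (days) | DCR shift (points) | PFS-4 |
|---|---|---|---|
| 5% | 1.4 to 2.8 | 1.0 | 62.9% to 63.7% |
| 10% | 2.8 to 5.6 | 2.1 | 62.9% to 64.5% |
| 20% | 5.6 to 11.2 | 4.1 | 62.9% to 66.2% |

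A simulation of the same model agreed to rounding.

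**The case against.** The strongest reply is that the SAP is silent, not contrary. No sentence in it says to use the confirming scan. SAP Section 1 says it is to be read with the protocol, and the SAP works from assessments as recorded. If a site applies 9.3.1 and re-enters the first scan as PD, the SAP rules return the original date and BOR is PD. The documents then agree. This stands, and it makes the problem conditional. It does not remove it, because neither document requires re-entry. Nor does reading the two together settle which rule a programmer follows: the SAP already departs from the protocol elsewhere, for example by starting PFS at randomization where protocol 10.4.2 starts it at initiation of therapy.

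The mRECIST scope is also narrower. No minimum repeat interval is stated, and a nodule of at least 1 cm with the typical vascular pattern is classed as HCC without a repeat scan. This stands too.

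Finally, there is no hypothesis test, anti-tumor activity is descriptive, and the gap applies to all arms alike. That limits the consequence, and nothing here shows a bias between arms. DCR is still a phase II primary endpoint and PFS-4 a named estimate, so their derivation should be fixed in advance.

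**Conclusion.** The gap is real and worth closing, and its effect is limited. Where a confirmed new lesion's first scan stays recorded as non-PD, the SAP as written dates PD later than the protocol does: by at least 28 days under RECIST 1.1, and nominally by 56 (42 to 70 with windows) if confirmation waits for the next scheduled scan. A week-8 scan left as SD also turns a protocol PD into disease control, at 3.3 points of DCR per patient in a 30-patient arm.

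A reader might infer more than the documents support:
- *That the trial's PFS runs 4 to 8 weeks long.* This is the nominal delay for one affected patient. Under the illustrative 5% to 20%, the arm mean moves by about 1 to 11 days.
- *That every affected patient moves DCR or PFS-4.* Only a week-8 first appearance recorded as SD or better, with no earlier SD or response, is shown here to move DCR. PFS-4 moves only when the two scans fall on either side of the cut-off.
- *That the error always favours DCR.* An NE entry at week 8 gives no such gain.
- *That PFS is inflated by 17% to 33%.* That divides one patient's 28 or 56 days by another trial's 5.5-month TTP (about 167 days). It is not an effect on this trial's estimate.

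The conclusion rests on first scans not being re-entered as PD. The documents give no frequency for such lesions and do not say how an equivocal scan is coded.

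**What to change.** Add to the PFS event row and note 2 of SAP Appendix 1.4: *If a new lesion first recorded as equivocal is confirmed on a later scan (Protocol 9.3.1, 9.3.2), the PD date is the date of the scan on which it was first seen, applied separately for RECIST 1.1 and mRECIST.*

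Add to SAP Appendix 1.3: *That scan is classed as PD for BOR.*

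Identify the first-seen scan from the RECIST and mRECIST worksheets that protocol 5.7.2 already requires. The documents mention no field for equivocal status, so send a site query where the worksheet does not show it.

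The cost is two sentences and a small derivation or query step. PFS and DCR may come out slightly less favourable, which is the result of applying the protocol's own rule.
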